## N-DOSE Protocol v3.1

The analysis of exploratory endpoints will be performed in a similar manner as for the primary and secondary endpoints. ANCOVA will be used to compare endpoints at week 12, and LME will be used to compare change from baseline to week 4, week 8 and week 12.

In addition, for PET analyses, changes in network scores with treatment will be evaluated for each group separately using permutation tests. Relationships between network values, brain NAD levels and MDS-UPDRS motor ratings or between treatment-related changes in these variables will be evaluated using Pearson's product-moment correlations, whereas Spearman rank-order correlation coefficients will be computed for non-normally distributed variables.

Omics data will undergo rigorous quality control and filtering according to established best practice procedures, as we have previously described. The between visit change in this data will be assessed by a pairwise comparison between each NR group and the placebo group, using linear models with appropriate covariates as we have previously described. Comparison of adverse events and abnormal laboratory test results between the treatment and placebo groups will be analyzed descriptively.

Further details for the analysis are outlined in the statistical analysis plan (SAP) for the trial, and we refer the reader to this document.

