	To compare the effect of orally administered NR in the DE-group versus DS-group on quality of life in PD at week 12.	Change in the EQ-5D-5L score.
	To assess the dose-response relationship between NR dose (1000 mg, 2000 mg, 3000 mg	Change in the EQ-5D-5L score.

N-DOSE Protocol v3.1

	per day) and changes in quality of life in PD from baseline to weeks 4, 8 and 12.	
Hypothesis-generating or resource-dependent endpoints (may be reported in follow-up or secondary publications).		
To compare the effect of orally administered NR in the DE-group versus DS-group on gene expression at week 12.	Change in gene expression, measured by RNA sequencing (RNAseq).	
To assess the dose-response relationship between NR dose (1000 mg, 2000 mg, 3000 mg per day) and changes in gene expression from baseline to weeks 4, 8 and 12.	Change in gene expression, measured by RNA sequencing (RNAseq).	
To compare the effect of orally administered NR in the DE-group versus DS-group on protein expression at week 12.	Change in protein levels, measured by LC-MS.	
To assess the dose-response relationship between NR dose (1000 mg, 2000 mg, 3000 mg per day) and changes in protein expression from baseline to weeks 4, 8 and 12.	Change in protein levels, measured by LC-MS.	
To compare the effect of orally administered NR in the DE-group versus DS-group on serum and CSF inflammatory markers at week 12.	Change in inflammatory cytokines in serum and CSF, measured by ELISA.	
To assess the dose-response relationship between NR dose (1000 mg, 2000 mg, 3000 mg per day) and changes in serum inflammatory markers from baseline to weeks 4, 8 and 12.	Change in inflammatory cytokines in serum, measured by ELISA.	
To compare the effect of orally administered NR in the DE-group versus DS-group on histone acetylation in PD at week 12.	Change in histone panacetylation, measured by immunoblotting.	
To assess the dose-response relationship between NR dose (1000 mg, 2000 mg, 3000 mg per day) and changes in histone acetylation in PD from baseline to weeks 4, 8 and 12.	Change in histone panacetylation, measured by immunoblotting.	
To compare the effect of orally administered NR in the DE-group versus DS-group on H3K27 and H4K16 histone acetylation in PD at week 12.	Changes in levels of H3K27 and H4K16 acetylation, measured by immunoblotting.	

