**KG2 – Confirm whether NR has a symptomatic clinical effect and assess its dose responsiveness.** The NADPARK and NR-SAFE studies showed that NR was associated with a clinical improvement, in the form of UPDRS decrease, and this correlated significantly with the increase in cerebral NAD levels and change in the brain metabolic network (NRRP). Furthermore, the clinical improvement was more pronounced with 3000 mg NR in the NR-SAFE study, compared to 1000 mg in the NADPARK study. These findings suggest that NR may be ameliorating neuronal function in PD, resulting in symptom improvement. Confirming this effect and assessing its dose-dependence will allow us to: **1)** determine the optimal clinical dose of NR in PD, and **2)** account for symptomatic effects in neuroprotection trials.

**KG3 – Determine the dose-dependence of the metabolic response to NR therapy.** The NADPARK study showed that a dose of 1000 mg NR daily augmented the NAD metabolome in PBMC, muscle and CSF. The NR-SAFE study suggested that a dose of 3000 mg NR daily leads to a more potent augmentation of the NAD metabolome in blood. The relationship between NR dose and metabolic response needs to be further explored in order to determine optimal dosing regimens.

**KG4 – Determine whether NR therapy enhance proteostasis in PD and characterize the dose dependence of this effect.** Impaired proteostasis plays a central role in PD and other neurodegenerative disorders, including Alzheimer's disease (AD) and amyotrophic lateral sclerosis (ALS). Our transcriptomic analyses in the NADPARK study indicated that NR therapy may enhance proteostasis by inducing the expression of both proteasomal and lysosomal pathways. If confirmed, this would suggest that NR targets

multiple major processes implicated in the pathophysiology of PD, including mitochondrial respiratory dysfunction, oxidative damage, lysosomal and proteasomal impairment, and neuroinflammation. Moreover, it is not known whether higher NR doses can induce stronger induction of proteostasis in PD.

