To assess the dose-response relationship between NR dose (1000 mg, 2000 mg, 3000 mg per day) and changes in quality of life in PD from baseline to weeks 4, 8 and 12.	Change in the EQ-5D-5L score.
Hypothesis-generating or resource-dependent endpoints (may be reported in follow-up or secondary publications).	
To compare the effect of orally administered NR in the DE-group versus DS-group on gene expression at week 12.	Change in gene expression, measured by RNA sequencing (RNAseq).
To assess the dose-response relationship between NR dose (1000 mg, 2000 mg, 3000 mg per day) and changes in gene expression from baseline to weeks 4, 8 and 12.	Change in gene expression, measured by RNA sequencing (RNAseq).
To compare the effect of orally administered NR in the DE-group versus DS-group on protein expression at week 12.	Change in protein levels, measured by LC-MS.

N-DOSE Protocol v3.1

To assess the dose-response relationship between NR dose (1000 mg, 2000 mg, 3000 mg per day) and changes in protein expression from baseline to weeks 4, 8 and 12.	Change in protein levels, measured by LC-MS.
To compare the effect of orally administered NR in the DE-group versus DS-group on serum and CSF inflammatory markers at week 12.	Change in inflammatory cytokines in serum and CSF, measured by ELISA.
To assess the dose-response relationship between NR dose (1000 mg, 2000 mg, 3000 mg per day) and changes in serum inflammatory markers from baseline to weeks 4, 8 and 12.	Change in inflammatory cytokines in serum, measured by ELISA.
To compare the effect of orally administered NR in the DE-group versus DS-group on histone acetylation in PD at week 12.	Change in histone panacetylation, measured by immunoblotting.
To assess the dose-response relationship between NR dose (1000 mg, 2000 mg, 3000 mg per day) and changes in histone acetylation in PD from baseline to weeks 4, 8 and 12.	Change in histone panacetylation, measured by immunoblotting.
To compare the effect of orally administered NR in the DE-group versus DS-group on H3K27 and H4K16 histone acetylation in PD at week 12.	Changes in levels of H3K27 and H4K16 acetylation, measured by immunoblotting.
To assess the dose-response relationship between NR dose (1000 mg, 2000 mg, 3000 mg per day) and changes in on H3K27 and H4K16 histone acetylation in PD from baseline to weeks 4, 8 and 12.	Changes in levels of H3K27 and H4K16 acetylation, measured by immunoblotting.

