To compare the effect of orally administered NR in the DE-group versus DS-group on the genomic distribution of H3K27 and H4K16 histone acetylation in PD at week 12.	Change in the genomic distribution of H3K27 and H4K16 acetylation, measured by chromatin immunoprecipitation sequencing (ChIPseq).
To assess the dose-response relationship between NR dose (1000 mg, 2000 mg, 3000 mg per day) and changes in the genomic distribution of H3K27 and H4K16 histone acetylation in PD from baseline to weeks 4, 8 and 12.	Change in the genomic distribution of H3K27 and H4K16 acetylation, measured by chromatin immunoprecipitation sequencing (ChIPseq).
To compare the effect of orally administered NR in the DE-group versus DS-group on folate and one-carbon metabolism in PD at week 12.	Change in folate and one-carbon metabolites in blood and CSF, measured by HPLC-MS.
To assess the dose-response relationship between NR dose (1000 mg, 2000 mg, 3000 mg per day) and changes in folate and one-carbon metabolism in PD from baseline to weeks 4, 8 and 12.	Change in folate and one-carbon metabolites in blood, measured by HPLC-MS.
To compare the effect of orally administered NR in the DE-group versus DS-group on methyl donors in PD at week 12.	Change in methyl-donors (e.g., SAM), measured by HPLC-MS, in the blood and/or CSF.
To assess the dose-response relationship between NR dose (1000 mg, 2000 mg, 3000 mg	Change in methyl-donors (e.g., SAM), measured by HPLC-MS, in the blood.

	per day) and changes in methyl-donors in PD from baseline to weeks 4, 8 and 12.	
	To compare the effect of orally administered NR in the DE-group versus DS-group on DNA methylation at week 12.	Change in level and genomic distribution of DNA methylation, measured by Illumina Infinium MethylationEpic kit.
	To assess the dose-response relationship between NR dose (1000 mg, 2000 mg, 3000 mg per day) and changes in methyl-donors in PD from baseline to weeks 4, 8 and 12.	Change in level and genomic distribution of DNA methylation, measured by Illumina Infinium MethylationEpic kit.
	To compare the effect of orally administered NR in the DE-group versus DS-group on synthesis of neurotransmitters in CSF at week 12.	Change in neurotransmitters in CSF, measured by HPLC-MS.
	Determine whether NR-therapy affects the gut microbiome in a dose-responsive manner at week 12.	Change in gut microbiome composition, measured by metagenomics in fecal samples.

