### 5.3 Methods for Continuous Exploratory Endpoints

As described in section 4.4, due to the nature of the exploratory outcomes, the analysis method is subject to change. The preliminary plan is that they will be analysed in the same manner as the primary endpoint if they have observations at V1, V2, V3 and V4 (see sections 5.1.2 and 5.1.7) and the same manner as the secondary endpoint if they only have observations at V1 and V4 (see sections 5.2.2 and 5.2.7).

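### The one omics-specific analysis rule (Protocol 10.4) compares each NR arm with placebo, which does not test dose dependence and conflicts with the omics objectives, other Protocol text and the SAP

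*Protocol*

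**What the plan says.** **The omics rule.** Protocol 10.4 has one sentence on how omics data will be compared: between-visit change will be "assessed by a pairwise comparison between each NR group and the placebo group, using linear models". It uses linear models with covariates chosen as in the group's earlier work. It names no DE–DS contrast and does not list which endpoints count as omics.

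**The objectives.** In the synopsis and Protocol section 2, a typical week-12 omics objective reads "To compare the effect of orally administered NR in the DE-group versus DS-group on gene expression at week 12". It is paired with a dose-response objective: "To assess the dose-response relationship between NR dose (1000 mg, 2000 mg, 3000 mg per day) and changes in gene expression". Protein expression, histone acetylation and DNA methylation follow the same pattern. The microbiome objective does not name the two arms but still asks about dose: "Determine whether NR-therapy affects the gut microbiome in a dose-responsive manner at week 12". In Protocol 1.4, the proteostasis gap ends with "it is not known whether higher NR doses can induce stronger induction of proteostasis in PD".

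**Other analysis text.** Earlier in Protocol 10.4 a general rule states: "The analysis of exploratory endpoints will be performed in a similar manner as for the primary and secondary endpoints". That means a DE–DS ANCOVA at week 12 plus a mixed model. Protocol 10.5 lists a DE–DS comparison, and then comparisons between and within all three arms, for a set of dependent variables that includes the omics measures. SAP 5.3 says of exploratory endpoints that "they will be analysed in the same manner as the primary endpoint if they have observations at V1, V2, V3 and V4", and that those measured only at V1 and V4 follow the CSF endpoint. Both routes give DE–DS and DS–placebo ANCOVAs adjusted for baseline and nothing else; the first adds a three-arm mixed model with DS as reference. SAP 4.4 and 5.3 both describe this as a preliminary plan open to change.

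**The concern.** A comparison of an NR arm with placebo has the null hypothesis that NR does nothing. It rejects for a flat response and for a rising one alike. Followed alone, the omics sentence cannot answer a DE–DS or dose-response objective.

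The only way to get at dose from its output would be to compare two sets of results: features significant for DE against placebo, and features significant for DS against placebo. That comparison is unreliable. The two tests have different power (40 against 20 people, and 20 against 20) and share a placebo arm. A feature with the same effect in both NR arms can reach significance in one and miss it in the other. At stake is whether statements that the higher dose does more to gene expression, proteostasis or methylation rest on a test of that question.

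**Working it through.** **1. The rules side by side**

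| Source | Contrasts | Covariates |
|---|---|---|
| Protocol 10.4, omics sentence | DE–PL, DS–PL | yes, unspecified |
| Protocol 10.4, general exploratory rule | DE–DS (ANCOVA), mixed model | as for primary: baseline only in the ANCOVA |
| Protocol 10.5, hypotheses | DE–DS; also all three arms | not stated |
| SAP 4.4/5.3 via 5.1.2, 5.1.7, 5.2.2, 5.2.7 | DE–DS and DS–PL (ANCOVA); three-arm mixed model for V1–V4 outcomes | ANCOVA: baseline only; mixed model: none added |

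The lists in SAP 4.4 name gene and protein expression, DNA methylation and the microbiome. They do not name histone acetylation, ChIP-seq or fecal metabolomics.

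**2. Inputs for the size of a misreading**

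The plan has no omics power figure to reproduce. Protocol 10.1 gives only a judgement that 20 per group suffices for proteomics and epigenomics, without an effect size or SD.
- Arm sizes: PL 20, DS 20, DE 40 (Protocol 4.2).
- Two-sided 0.05 (SAP 2.3.2).
- Assumption: a flat dose response, with DE and DS both d SD above placebo. The documents give no d, so a range is shown.

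**3. Formulas**

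Standard errors, in SD units:
- DE–PL: √(1/40 + 1/20) = 0.274
- DS–PL: √(1/20 + 1/20) = 0.316
- DE–DS: √(1/40 + 1/20) = 0.274

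Correlation of the two placebo contrasts: (1/20)/(0.274 × 0.316) ≈ 0.58. The chance of a feature being significant in DE only is P(|Z₁| > 1.96 and |Z₂| ≤ 1.96) for a bivariate normal with means d/0.274 and d/0.316 and that correlation.

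**4. Results when there is no dose effect**

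| d | DE–PL significant | DS–PL significant | DE only | DS only | DE only if arms were 20/20/20 |
|---|---|---|---|---|---|
| 0.5 | 44.7% | 35.3% | 19.8% | 10.4% | 15.4% |
| 0.6 | 59.1% | 47.5% | 21.6% | 10.0% | 16.6% |
| 0.8 | 83.2% | 71.6% | 17.8% | 6.2% | 13.9% |
| 1.0 | 95.5% | 88.5% | 9.2% | 2.3% | 7.5% |
| 1.25 | 99.5% | 97.7% | 2.2% | 0.3% | 1.9% |
| 1.5 | 100.0% | 99.7% | 0.3% | 0.0% | 0.3% |

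A simulation of 40,000 trials with t tests agrees. DE only was 20.0%, 19.2% and 10.5% at d = 0.5, 0.8 and 1.0, and the direct DE–DS test rejected in 5.0–5.1%.

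**5. What the allocation contributes**

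Against equal arms, 40 v 20 adds 19.8 − 15.4 = 4.4 points at d = 0.5, 17.8 − 13.9 = 3.9 at 0.8 and 9.2 − 7.5 = 1.7 at 1.0. It also makes the discordance favour DE. Most of the discordance would exist without it.

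**6. A stricter threshold**

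At an assumed p < 0.0001, the discordance moves to larger effects: DE only is 28.0% against 5.5% for DS only at d = 1.25, 16.1% at 1.5 and 0.7% at 2.0.

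**7. What the direct contrast can detect**

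Per feature at 0.05: (1.96 + 0.842) × 0.274 = 0.77 SD at 80% power, and (1.96 + 1.282) × 0.274 = 0.89 SD at 90%.

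**The case against.** The strongest reply is that the DE–DS test is already planned. A reader of the omics sentence might infer that omics will be compared with placebo only. The documents do not support that: the general rule in the same section, Protocol 10.5 and SAP 4.4 and 5.3 all lead to DE–DS, and Protocol 10.4 refers to the SAP for detail. Nor is every omics objective worded as DE versus DS; the microbiome one is not, and many are paired with dose-response objectives. Several knowledge gaps in Protocol 1.4 ask first whether NR has an effect at all, and placebo is the right comparator for that.

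A reader might also infer that a flat dose response would be reported as a dose effect. That needs a rule for judging dose by comparing the two sets of placebo results, and no passage states one. The figures above depend on it and on assumed effect sizes. Protocol 10.1 expects large transcriptomic effects, for which the discordance at 0.05 is small; for proteomic and epigenomic data it has no earlier results to go on.

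All of this stands, and it limits the point to a conflict between rules. It does not remove the conflict. A specific rule that follows a general one is normally taken to govern its own subject. The two also differ on covariates, so they cannot simply be merged. The SAP does not settle precedence, because it leaves its exploratory methods open and does not name some of the omics endpoints.

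**Conclusion.** The point holds as an unresolved inconsistency, not as a missing analysis. Two analysts could follow different rules, test different hypotheses on the same omics data, and both claim to have kept to the plan. Only one of those rules answers the dose question.

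The possible harm is moderate and conditional. It arises only if dose is read from the placebo contrasts, and its size rests on assumed flat effects with normal errors. At 0.05 it is largest for moderate effects, with DE-only discordance peaking near 22% at 0.6 SD among the values tried. A stricter omics threshold would shift that peak to larger effects.

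The severity is minor. Gene, protein, histone, methylation and microbiome endpoints are classed as hypothesis-generating. The primary endpoint and the CSF NAD metabolome have their own explicit DE–DS ANCOVAs.

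**What to change.** Amend the omics sentence in Protocol 10.4 and align SAP 5.3:
- Test dose dependence of each omics feature by the direct DE–DS contrast from one baseline-adjusted linear model containing all three arms, and state its covariates once for both documents.
- Keep DE–PL and DS–PL from the same model as evidence of an NR effect only.
- State that dose dependence will not be inferred from the number or overlap of features significant against placebo.
- List the endpoints covered, including histone acetylation, ChIP-seq and fecal metabolomics, which SAP 4.4 does not name.

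The cost is wording and one extra contrast, with no new patients, samples or visits. The DE–DS standard error equals that of DE–PL, so the contrast is no less precise than the better of the two placebo comparisons. The downside is that fewer features may be reported as dose-dependent.

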## 10.5 Statistical Analysis

### Dependent variable

Primary analysis:

- Cerebral NAD levels (measured by P-MRS)

Secondary, exploratory and safety analyses:

- Adverse events, categorized as either moderate or severe.
- Levels of CSF NAD and NAD-metabolites (measured by LC-MS).
- Levels of NRRP expression (measured by FDG-PET)
- Levels of PDRP expression (measured by FDG-PET)
- Routine blood tests
- Total MDS-UPDRS
- MDS-UPDRS Part I
- MDS-UPDRS Part II
- MDS-UPDRS Part III
- MDS-UPDRS Part IV
- MDS-NMS
- MoCA
- GIDS-PD
- EQ-5D-5L
- Levels of NAD-related and other metabolites in PBMC, frozen blood, urine and CSF
- Expression of RNA and protein of genes and pathways involved in proteasomal and lysosomal biogenesis and function.
- Histone panacetylation levels
- Levels of specific lysine residues H3K27 and H4K16 acetylation

## N-DOSE Protocol v3.1

- Genome-wide distribution of histone lysine residues found to be quantitatively altered by the treatment (measured by ChIP-Seq).
- Level of inflammatory cytokines in patient serum and CSF.
- Gene and protein expression levels in PAXgene blood.
- Levels of one carbon metabolism metabolites, measured by HPLC-MS metabolomics in PBMC and CSF.
- Levels of monoamine neurotransmitters in CSF.
- Levels and genomic distribution of DNA methylation.
- Gut microbiome composition.
- Fecal metabolomics, including fatty acid levels.
- Sense of smell, measured by B-SIT.

### **Statistical hypothesis**

Primary analysis:

- Our primary null hypothesis ( $H_0$ ) is that the NR-induced increases in cerebral NAD levels (measured by  $^{31}\text{P}$ -MRS) is not dose-responsive. The alternative hypothesis ( $H_A$ ) is that this increase is dose responsive.

Secondary analysis:

- Mean change between the NR dose escalation arm and NR 1000 mg arm for the dependent variables mentioned above.
- Mean change between and within the NR dose escalation arm, NR 1000 mg arm and placebo arm for the dependent variables mentioned above.

## **11 STUDY MANAGEMENT**

### **11.1 Investigator Delegation Procedure**

The principal investigator is responsible for making and updating a “delegation of tasks” listing all the involved co-workers and their role in the project. He will ensure that appropriate training relevant to the study is given to all of these staff, and that any new information of relevance to the performance of this study is forwarded to the staff involved.

### **11.2 Protocol Adherence**

Investigators ascertain they will apply due diligence to avoid protocol deviations.

All significant protocol deviations will be recorded and reported in the Case Report Form (CRF).

### **11.3 Study Amendments**

If it is necessary for the study protocol to be amended, the amendment and/or a new version of the study protocol (Amended Protocol) must be notified to and the Ethics Committee according to EU and national regulations.

### **11.4 Audit and Inspections**

Authorized representatives of the Ethics Committee may visit the center to perform inspections, including source data verification. Likewise, the representatives from the sponsor may visit the center to perform an audit. The purpose of an audit or inspection is to systematically and independently examine all study-

related activities and documents to determine whether these activities were conducted, and data were recorded, analyzed, and accurately reported according to the protocol, Good Clinical Practice (ICH GCP), and any applicable regulatory requirements. The principal investigator will ensure that the inspectors and auditors will be provided with access to source data/documents.

## **12 ETHICAL AND REGULATORY REQUIREMENTS**

The study will be conducted in accordance with ethical principles that have their origin in the Declaration of Helsinki and are consistent with ICH/Good Clinical Practice and applicable regulatory requirements. Registration of patient data will be carried out in accordance with national personal data laws.

